3. ABBREVIATIONS

AR	Adverse Reaction						
AE	Adverse Event						
CCR	Clinical Complete Regression						
CI	Chief Investigator						
CNC	Clinical No Change						
CPD	Clinical Progressive Disease						
CPR	Clinical Partial Regression						
CR	Complete regression						
eCRF	Electronic Case Report Form						
DMC	Data Monitoring Committee						
GCP	Good Clinical Practice						
IMP	Investigational Medicinal Product						
LM	Lentigo maligna						
LMM	Lentigo maligna melanoma						
MHRA	Medicines and Healthcare products Regulatory Agency						
NHS	National Health Service						
PCR	Pathological Complete Regression						
PNC	Pathological No Change						
PPD	Pathological Progressive Disease						
PPD	Pathological Partial Disease						
PI	Principal Investigator at a local centre						
REC	Research Ethics Committee						
R&D	Research and Development department						
SAE	Serious Adverse Event						
SAR	Serious Adverse Reaction						
SmPC	Summary of Product Characteristics						
SUSAR	Suspected Unexpected Serious Adverse Reaction						
TMG	Trial Management Group						
TSC	Trial Steering Committee						
WTCRF	Wellcome Trust Clinical Research Facility						

4. STUDY DESIGN

4.1. Overview

This is a multicentre, open label, non-randomised, single-stage trial to discriminate between a pathological CR rate of <60% and >85%. It is anticipated that approximately fourteen recruiting centres will take part.

[figure not shown]
A maximum of forty patients with lentigo maligna (LM) will undergo clinical lesion mapping (map 1) followed by 12 weeks topical imiquimod treatment. The dose of imiquimod will be adjusted according to local toxicity. Scheduled study visits during treatment will be at 1, 2, 4, 8 and 12 weeks. At these visits, tolerability and adverse reactions will be recorded with the aid of patient diaries. Any unscheduled consultations for dose adjustments will be recorded. After treatment, clinical response will be determined and the LM will be remapped if there is contiguous pigmentation outside the previously mapped area (map 2). This visit will be at 10 to 12 weeks after the last application of imiquimod. All patients will progress to biopsy, then surgical excision. This will include map 1 in all patients, and map 1 plus map 2 in those with pigmentation outside map 1, plus a margin of apparently healthy tissue. The entire specimen will be sectioned and examined histologically to determine pathological clearance and the presence of LM outside the mapped area. Patients who withdraw from imiquimod treatment prior to 12 weeks will still require surgical excision. This will be done at least 12 weeks after the first application of imiquimod and 10 to 12 weeks after the last application of imiquimod and 10 to 12 weeks after the last application of imiquimod and 10

The immune response against melanocyte differentiation antigens will be measured by ELIspot assays using blood samples drawn at baseline and the week 12 visit.

An overview of the study design is shown in figure 1.

Figure 1

Flow diagram showing progression of participants through the study.

Schedule of Assessments Table

Week	Pre- study	Baseline -1	0	1	2	4	8	12	22-24 (Post TX)		1-2 wks post SX	12 wks post SX
Biopsy	Х								X			
Informed consent		Х										
Pregnancy test		Х										
Medical history		Х										
Demographic data		Х										
Mapping of lesion		Х							Х	S		
Photograph lesion		Х							Х	C		
Blood samples for		X						x				
immune assay		^						^		ス		
Blood Sample for HLA		X								-		
typing		~								G		
User Opinion										_		Х
Questionnaire										Π		~
Study drug administered			Х	Х	Х	х	Х	Х		ת		
Study diary			Х	Х	Х	Х	Х	Х		\prec		
Adverse event			Х	Х	х	х	х	x				
recording			Λ	~	^	^	^	^				
Concomitant			х	х	х	х	х	x				
medications recording			Λ	^	^	^	^	^				
Collect unused drug/								x				
drug accountability								~				
Histological report											Х	
Definition of											х	
pathological response												

Please refer to section 9.0 for full requirements of study visit schedule and procedures.

5. SYNOPSIS

Title	Effect of topical imiquimod on lentigo maligna.
Acronym	LIMIT-1
Short title	Lentigo maligna imiquimod trial
Chief Investigator	[name]
Objectives	 Primary objective: To establish the pathological complete regression (CR) rate for lentigo maligna following topical treatment with imiquimod Secondary objectives: To define the accuracy of the clinical assessment of response after imiquimod treatment using visual assessment and biopsy To investigate the tolerability of imiquimod treatment To investigate the NHS resource associated with imiquimod treatment To determine whether imiquimod therapy might vaccinate against melanoma To establish patient treatment preferences for future trial design
Trial Design	A multicentre, open label, non-randomised, single-stage trial
Setting	Secondary care – local and specialist skin cancer multidisciplinary teams
Number of participants	40
Main eligibility criteria	 Clinical diagnosis of lentigo maligna (LM) Histological findings consistent with LM The upper limit of the lesion is not defined by size, but must be suitable for complete surgical excision using a 5 mm lateral margin. The outline of the lesion must be easily defined visually in daylight around its entire circumference. Patient fit enough and willing to undergo surgery as required by the protocol.
Study interventions	Topical imiquimod to lesional skin plus 2 cm for 12 weeks, then surgical excision

Duration of study	The patient will be in the study for a maximum of 36 weeks. This trial is estimated to last a total of 68 weeks, from initiation of the (first) study site to completion of the last patient.						
Randomisation and blinding	None						
Outcome	Primary outcome measure:						
measures	 Pathological complete regression (PCR) in the mapped biopsied and resected LM using 2 mm slices. 						
	Secondary outcome measures:						
	Clinical assessment of response after imiquimod treatment						
	Clinical feasibility of imiquimod treatment						
	Number of consultations with NHS staff during imiquimod treatment.						
	Frequency of functional T cell responses recognising peptide epitopes in melanocyte differentiation and cancer-testis antigens.						
	 Measurement of hypothetical treatment preferences for surgery or imiquimod for LM using standard gamble technique. 						

6. STUDY BACKGROUND AND RATIONALE

Lentigo maligna (LM) is an early form of melanoma usually located on chronically sunexposed skin in the over 50's. Characteristically, it presents as a slowly developing flat pigmented patch with gradual enlargement on the skin surface over several years. At this stage it is harmless because the cancer is confined to the outer layer of the skin. However, there is a significant, but poorly quantified risk of progression to invasive lentigo maligna melanoma (LMM) (1) which is accompanied by risk of the cancer spreading. Like other types of melanoma, the incidence of LM is increasing; in the South West of the UK incidence is estimated at 3.3 per 100,000 population per year (source: South West Public Health Observatory Cancer Intelligence Service, 2007); in the West Midlands at 3.0 per 100,000 per year (source: West Midlands Cancer Intelligence Unit, 2007). In both areas this has increased by more than 50% between 1993 and 2003. LM is no longer considered a disease of the elderly as the age of onset is decreasing.

Due to the nature of LM, effective early treatment is important. The current standard treatment for LM in the UK is surgery to completely remove the lesion with a safety margin of normal appearing skin. Surgery has a cure rate at 5 years of over 90% in unselected patients (2). Although effective, this invasive procedure is stressful and unpleasant to undergo. The head and neck is the most common site for LM and so surgery can produce significant functional and cosmetic disability. The surgical margin required for 95% cure rates is unclear, though is unlikely to be over 10 mm and may be as little as 2 mm (2,3). Although treatment failures are uncommon with surgery, when they do occur, multiple further operations are frequently required, and many treatment failures are never cured. Therefore an alternative, non-surgical treatment for LM is sought.

Other currently used treatments include radiotherapy, laser ablation, cryotherapy and more recently imiquimod (4-10). There is some evidence for efficacy of radiotherapy, but all reported studies are retrospective, numbers are small and it has not yet been compared with surgery. Cure rates vary from 86% to 100%, and treatment seems well tolerated. Cryotherapy is generally felt to be much less effective because LM frequently involves skin appendages, requiring treatment to be effective to a depth of several mm: there are reports of invasive melanoma following apparently effective cryotherapy. Similar reservations apply to laser treatment.

Imiquimod is an immune response modifier and binds to Toll-like receptor-7 (TLR-7). It is manufactured as a 5% cream (Aldara[™]) and is currently licensed for the treatment of actinic keratosis, superficial basal cell carcinoma and genital warts. Whilst the exact mechanism of action is not known, when used to treat pre-cancerous lesions and skin cancers, imiquimod results in inflammation, which destroys the lesion and can result in complete regression (CR).

Imiquimod is a topical treatment that has significant potential as a first line treatment for LM for several reasons:

- it may avoid the cosmetic and functional disabilities resulting from surgery or radiotherapy
- it may have potential significant cost saving for the NHS as surgery and radiotherapy are resource-intensive treatments

• it can be applied by the patient at home and so may reduce the inconvenience of accessing surgery and radiotherapy

In addition, if effective, imiquimod would be a very attractive treatment option if it were shown to result in an immune response that might protect against invasive melanoma in the future.

Given these potential advantages, imiquimod is increasingly being used off label by dermatologists in the UK. There have been several recent reports of topical treatment with imiquimod (8-14). Whilst the evidence for efficacy is striking with response rates of 77-90% being reported, our own unreported observations suggest that significant numbers may not respond to treatment, and published response rates may reflect reporting bias (15). There is no systematic evidence-base from clinical trials to support this use and so the place of this new treatment requires definition before it becomes firmly embedded in clinical practice (16-19). If it is shown to be safe and effective, understanding the mechanism of action could have major significance for the future management of other types of melanoma.

The results of this study will allow recommendations to be made regarding the use of imiquimod for LM and inform the need for a further definitive randomised trial. A low cure rate or residual sub-clinical disease which could allow LMM to develop undetected would mean a recommendation that imiquimod should not be used as a primary treatment for LM. However, if imiquimod is effective and safe, it is likely to have a role in the management of LM and further research would be warranted. A definitive randomised controlled trial would compare imiquimod with surgery to define CR duration. This approach depends critically on this method of assessment of CR being accurate; this is assessed in this trial. Furthermore, a positive outcome from this study may lead to evaluation of imiquimod as a treatment for other types of melanoma. If the two approaches were equivalent for long term cure of LM, use of imiquimod for LM might spare the majority of patients from surgery and reduce NHS resource use.

7. STUDY PURPOSE AND OBJECTIVES

7.1. Purpose

The purpose of this study is to determine whether imiquimod is a sufficiently effective treatment for lentigo maligna to progress to a randomised controlled trial (RCT) which would compare imiquimod with the current standard treatment (surgery).

This study will not determine treatment strategy; instead it is a tool to help make a decision about whether to proceed to a RCT. The subsequent RCT would then fully define the role of imiquimod in treating lentigo maligna. The use of imiquimod as a primary treatment could spare patients from undergoing potentially disfiguring surgery.

7.2. Primary Objective

To establish the pathological complete regression (CR) rate for lentigo maligna following topical treatment with imiquimod.

7.3. Secondary Objectives

- To define the accuracy of the clinical assessment of response after imiquimod treatment using visual assessment and biopsy
- To investigate the tolerability of imiquimod treatment
- To investigate the NHS resource associated with imiquimod treatment
- To determine whether imiquimod therapy might vaccinate against melanoma
- To establish patient treatment preferences for future trial design

8. Selection and Recruitment of Participants

8.1. Participants

Adults aged at least 45 years with lentigo maligna presenting to secondary care will be considered for this study.

8.2. Setting

40 participants will be recruited from approximately fourteen hospitals in the UK over an 8 month recruitment period.

8.3. Recruitment

Patients will initially be approached by a member of their treating team, which may include the investigator. If the patient is interested in finding out more about the study, they will agree to their details being passed to a member of the study team and be referred for further discussion.

If needed, the usual hospital interpreter and translator services will be available to assist with discussion of the trial, the participant information sheets, and consent forms, but the consent forms and information sheets will not be available printed in other languages. It will be explained to the potential participant that entry into the trial is entirely voluntary and that their treatment and care will not be affected by their decision. It will also be explained that they can withdraw at any time but attempts will be made to avoid this occurrence. In the event of their withdrawal it will be explained that their data collected so far will be retained and used as part of the study analysis.

8.4. Inclusion criteria

- Clinical diagnosis of lentigo maligna (LM) (acquired pigmented macule present for more than 12 months with no change in skin surface texture or contour, no palpability, diameter >10 mm, sited on the head or neck). The lower anatomical limit is the root of the neck – a line joining the medial end of the clavicles with the medial insertion of trapezius.
- Histological findings consistent with LM (increased numbers of atypical melanocytes confined to the epidermis, sun damaged skin) in one or more 4mm punch biopsies(s) from the darkest area, reported by a pathologist with expertise in

the diagnosis of melanocytic lesions, and part of a recognised NHS skin cancer Multi-Disciplinary Team.

- The upper limit of the lesion is not defined by size, but it must be suitable for complete surgical excision using a 5 mm lateral margin.
- The outline of the lesion must be easily defined visually in daylight around its entire circumference.
- Patient fit enough and willing to undergo surgery as required by the protocol.

8.5. Exclusion criteria

The following criteria will exclude the patient from the study:

- Clinical or histological evidence of invasive melanoma including any palpability of the lesion, or clinical and/or histological evidence of regression or dermal invasion
- Aged less than 45 years
- Recurrent LM the index lesion must not have been previously treated
- Life expectancy of less than 12 months
- Other skin lesions which may compromise the ability to complete this study, such as co-existing or adjacent melanoma or non-melanoma skin cancer. Co-existing adjacent actinic keratoses would not exclude the patient from the study
- Women of childbearing potential, who are pregnant, plan to become pregnant during their study participation or breastfeeding.
- Hypersensitivity to imiquimod or to any of the excipients (methylhydroxybenzoate (E218), propylhydroxybenzoate (E216), cetyl alcohol and stearyl alcohol).
- Taking immunosuppressive medication.
- Taking part in any other intervention study.
- Unable to give informed consent.

8.6. Informed consent

All participants will provide written informed consent before taking part in the study. When the patient is given the diagnosis of LM, and if the patient is potentially eligible, the study will be explained by their treating team (which may include the investigator). Patients will be given the study patient information leaflet to take home and read. If they are willing to participate, they will be asked to return to discuss the study further and in detail with the Investigator or co-investigator. They will answer any questions that the participant has concerning study participation.

The informed consent form will be signed and dated by the participant before they enter the trial and countersigned by the person explaining the study to the patient and taking the consent. One copy of the consent form will be kept by the participant, one will be kept by the Investigator and one copy will be retained in the patient's hospital records.

Should there be any subsequent amendment to the final protocol, which might affect a participant's participation in the trial, continuing consent will be obtained using an amended consent form which will be signed by the participant.

9. Details of Study Visit Schedule and Procedures

9.1. Pre-study phase

Diagnosis

Diagnosis of LM will be confirmed following biopsy by a specialist skin histopathologist and by clinico-pathological correlation. The biopsy will be one or more 4mm punch biopsies(s) from the darkest area. Surplus diagnostic material (1 H&E stained slide with three levels) will be required by the study histopathologist. This diagnostic slide will be sent by same day courier to the study histopathologist along with the post treatment specimens. The appropriateness of surgery will be confirmed by case review by a skin cancer multi-disciplinary team meeting. The patient will then be given the diagnosis of LM, a pre-check for eligibility will be made and, if appropriate, the study will be explained and the patient offered the chance to participate. Patients will then be given the study patient information leaflet to take home and read.

Baseline visit (week -1)

The patient will be given the opportunity to have a further discussion about the study and receive answers to any questions they may have. The patient will give their written informed consent to take part in the study. The investigator will confirm that the patient is eligible to enter the study, a medical history will be taken and demographic data collected. Before treatment is started, the patient's General Practitioner will be contacted to inform them about their patient's involvement with study, details of the study and the potential local toxicity of imiquimod.

The area of skin involved in the LM will be defined by using temporary surgical skin marking ink, and small point tattoos on the outline of the lesion at 4 sites on its periphery at 12, 3, 6 and 9 o'clock, using established methods for defining radiotherapy treatment sites. The size of the LM will be measured in mm using the largest diameter and its perpendicular. The map will be made under adequate artificial lighting and standardised magnification. The outline of the lesion will be traced onto a transparent sheet, known as 'map 1'. Therefore, map 1 defines the pre-treatment lesion.

A standardised (i.e. same camera, setting and distance) digital clinical photograph of the outlined lesion will be taken as a baseline, pre-treatment reference.

Blood samples will be taken before treatment starts and after the treatment finishes to find out if the imiquimod treatment has resulted in an immune response. Some of the blood taken at this visit is also used for HLA typing.

At this visit two blood samples are taken, 10ml in EDTA tubes and 50ml sodium heparin tubes, and are sent by same day courier to the scientific study centre in Birmingham at the address below (refer to section 13 for further details).

[name] Wellcome Trust Clinical Research Facility (WTCRF) University Hospitals Birmingham NHS Foundation Trust Queen Elizabeth Hospital, [name] [contact] The investigator site should inform the WTCRF that a sample is to be taken, giving 48 hours notice preferably. Samples should not be sent on a Friday if possible.

Female participants of childbearing potential will be required to have a negative pregnancy test.

Approved site personnel will enrol the patient into the study using the online eCRF. A trial number will be allocated for the participant. The local investigator will then complete a study specific prescription including the patient trial number. The local pharmacy will dispense sufficient imiquimod as required by each participant, taking into account any dose adjustments made during treatment visits.

9.2. Treatment phase

Week 0

The date of the first application of imiquimod will be day 1, week 0. Day 1 will be a Monday to facilitate adherence; imiquimod will be applied Monday to Friday with no treatment on Saturday and Sunday. The co-ordinating centre will ensure the investigator is aware of this date as this becomes the reference point for scheduling subsequent treatment phase visits.

Participants will be instructed to apply imiquimod for 12 weeks to the lesion plus a 20 mm margin of surrounding normal skin.

Participants will be asked to keep a study diary during the treatment phase (starting from day 1, week 0) and to bring to each clinic visit to be used as an aide memoir during the consultation. The following information will be recorded in the diary:

- Whether participants have applied imiquimod
- If not whether this was a scheduled day off, or missed due to toxicity .
- The response to "How acceptable have you found the imiquimod treatment over the past week?" answered on a 10cm visual analogue scale ranging from totally acceptable to totally unacceptable
- The name of any topical treatment used on the LM other than imiquimod
- If any of the following adverse reactions have occured:
 - Local reactions redness, swelling, discomfort or pain at the site of application
- There will be space for participants to record anything else they feel is important or that they would like to discuss with the investigator.

Weeks 1, 2, 4 and 8

Scheduled clinic visits will be at 1, 2, 4, 8 weeks after the start of treatment. At these visits, the following will be recorded:

- The contents of the patient daily diary will be reviewed and checked for completeness, and a new diary issued
- The investigator will rate the local site reaction on the following scale:
 - o **none**

- o mild reaction (slight redness, discomfort, no swelling, no ulceration)
- o moderate reaction (redness, pain and swelling, no ulceration)
- o severe reaction (redness, pain, swelling and ulceration)
- The participant will be specifically asked about any flu like symptoms they have experienced since the last visit. If present, these will be documented on the AE eCRF.
- The dose of imiquimod will be adjusted according to the following algorithm:

If intolerable at 5 days per week; stop completely for 1 week then restart but at a reduced dose of 3 days per week. Increase to 5 days per week as soon as tolerable.

If intolerable at 3 days per week, a further week off, start again at 3 days per week. Stop if intolerable.

If 5 days per week is tolerated increase to 7 days per week. If intolerable repeat algorithm as before.

• Any other new medication usage and health service usage data will be recorded using the diary as an aide memoir.

If treatment of the LM with imiquimod is stopped because of local toxicity, this will prompt an unscheduled clinic visit so that the dose adjustment algorithm can be implemented.

If at any point during the treatment phase, the lentigo maligna is judged to have progressed to invasive melanoma then the patient will progress immediately to surgery. Simple enlargment of the LM macular area does not count as progression to invasive melanoma.

Week 12

At this final scheduled treatment phase visit, the following will be recorded:

- Adverse reaction data at the application site will be recorded from the participant diary and discussion with the participant. The investigator will rate the local site reaction on the following scale:
 - o **none**
 - o mild reaction (slight redness, discomfort, no swelling, no ulceration)
 - o moderate reaction (redness, pain and swelling, no ulceration)
 - o severe reaction (redness, pain, swelling and ulceration)
- Imiquimod treatment will stop at this point.
- The participant will be specifically asked about any flu like symptoms they have experienced since the last visit. If present, these will be documented on the AE eCRF.
- Any new medication usage and health service usage data will be recorded using the diary as an aide memoir.
- All unused medication will be returned and quantified.
- The final diary will be collected.

At this visit the post-treatment blood sample for the immune response is taken, 50ml sodium heparin tube, and is sent by same day courier to the scientific study centre in Birmingham at the address below (refer to section 13 for further details).

[name] Wellcome Trust Clinical Research Facility (WTCRF) University Hospitals Birmingham NHS Foundation Trust Queen Elizabeth Hospital, [name]

[contact]

The investigator site should inform the WTCRF that a sample is to be taken, giving 48 hours notice preferably. Samples should not be sent on a Friday if possible.

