11.2. Definitions

All AEs, as defined by the protocol, occurring during the trial will be reported and documented as described below in terms of seriousness, severity and causality.

For the purposes of this study an AE only includes:

1. any study drug related event as listed above in section 11.1

2. any condition detected or diagnosed after medical product has been administered and has a possible, probable or definite causal relationship with the study drug.

An AE does not include a / an:

1. medical or surgical procedure (e.g., surgery, endoscopy, tooth extraction, transfusion); but the condition that leads to the procedure is an AE.

- 2. pre-existing disease or conditions present or detected at the start of the study that did not worsen.
- 3. situations where an untoward medical occurrence has not occurred (e.g., hospitalisations for cosmetic elective surgery, social and / or convenience admissions).
- 4. disease or disorder being studied or sign or symptom associated with the disease or disorder unless more severe than expected for the participant's condition.
- 5. overdose of concurrent medication without any signs or symptoms.

A **Serious Adverse Event (SAE)** is any adverse event as defined by the protocol that results in any of the following outcomes:

- Death
- Life-threatening
- Inpatient hospitalisation or prolongation of existing hospitalisation
- Persistent or significant disability / incapacity
- A congenital anomaly or birth defect in the offspring of a participant
- Other medical events may be considered to be a SAE if they require medical or surgical intervention to prevent one of the outcomes listed in this definition.

An adverse event whose causal relationship to the study drug is assessed by the Chief Investigator as "possible", "probable", or "definite" is an Adverse Reaction (AR). If the AR is classed as serious then it is a Serious Adverse Reaction (SAR). A distinction is drawn between serious and severe AEs. Severity is a measure of intensity whereas seriousness is defined using the criteria above. Hence, a severe AE need not necessarily be serious.

A serious adverse event that is either sudden in its onset, unexpected in its severity and seriousness or not a known side effect of the Investigational Medicinal Product (IMP) and related or suspected to be related to the IMP is classed as **Suspected Unexpected Serious Adverse Reaction (SUSAR)** and requires expedited reporting as per the clinical trials regulations.

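### The week 1 flu-like symptom question reaches back before the first dose, and neither flu-like symptoms nor the local reaction grade is recorded before treatment

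*Protocol*

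**What the plan says.** Section 4.1 of the protocol sets the treatment-phase visits: "Scheduled study visits during treatment will be at 1, 2, 4, 8 and 12 weeks". Section 9.2 describes week 0 only as a date: "The date of the first application of imiquimod will be day 1, week 0". The diary also starts on that day, and its adverse reaction prompt covers local reactions only.

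At each visit from week 1 to week 12, section 9.2 requires two things that matter here. The first is a question with a look-back: "The participant will be specifically asked about any flu like symptoms they have experienced since the last visit". What follows from a positive answer is stated as "If present, these will be documented on the AE eCRF", with no condition on when the symptom began. The second is a grade from none to severe, made at the visit: "The investigator will rate the local site reaction on the following scale".

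For the baseline visit at week -1, section 9.1 says "a medical history will be taken and demographic data collected", and adds mapping, four point tattoos and blood samples. A "digital clinical photograph of the outlined lesion will be taken as a baseline, pre-treatment reference". Neither the flu-like question nor the reaction scale appears there.

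Section 11.2 restricts adverse events to listed drug-related events, or to conditions found after administration with at least a possible causal link. It excludes "pre-existing disease or conditions present or detected at the start of the study that did not worsen".

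**The concern.** The trial has one arm, so each patient's own pre-treatment state is the only reference for tolerability, which is a secondary objective. Aching, fatigue and malaise are common and non-specific. The mild grade of the local scale needs only slight redness and discomfort. The skin being graded is sun-damaged, has had at least one punch biopsy, receives tattoos at week -1, and may lie next to actinic keratoses, which section 8.5 allows. Without the same items recorded before dosing, the exclusion of unchanged pre-existing conditions is hard to apply to these symptoms.

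The data would never be collected, so no later analysis plan could restore them. Section 16.1 allows highly adverse secondary outcomes to weigh against a randomised trial even if the primary objective is met. An inflated reaction count is therefore not entirely harmless.

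**Working it through.** The plan gives no figure on this point to reproduce. The check is a comparison of sections, followed by a bound on the size.

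**1. The first recall window.** The visits in the text are week -1 (9.1) and weeks 1, 2, 4, 8 and 12 (4.1). At week 1 the last visit is therefore week -1. The window is about two weeks, and one of them is before the first application: 1/2 = 50%. Over all recall from week -1 to week 12, the pre-dose share is 1/13 = 8%.

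**2. Which measures are affected.** The look-back wording belongs to the flu-like question only. The local grade is made at the visit, and diary data on local reactions start on day 1. For the local reaction the gap is the missing baseline grade, and there is no reach-back.

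**3. Section 9.2 against section 11.2.** Section 9.2 sends any reported flu-like symptom in the window to the adverse event form. Section 11.2 admits only drug-related or post-administration events. The two do not match for the pre-dose week.

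**4. Size of the pre-dose week.** The documents give no background rate, so rates are assumed and a range is shown. There are 40 patients (section 16.1), and symptoms are taken as independent between periods.

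(a) Weekly background rate r. Patients ever reporting over 13 weeks are 40[1-(1-r)^13]. Without the pre-dose week they are 40[1-(1-r)^12]. Patients with a symptom in the pre-dose week itself are 40r.

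| r | 40r | 13 weeks | 12 weeks | difference |
|---|---|---|---|---|
| 1% | 0.4 | 4.9 | 4.5 | 0.4 |
| 2% | 0.8 | 9.2 | 8.6 | 0.6 |
| 5% | 2.0 | 19.5 | 18.4 | 1.1 |
| 10% | 4.0 | 29.8 | 28.7 | 1.1 |

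(b) Rate p per recall window, five windows, with half of the first window's risk falling before the dose. Ever reporting is 1-(1-p)^5. With the pre-dose half removed it is 1-(1-p)^4(1-p/2).

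| p | all five windows | pre-dose half removed | difference x 40 |
|---|---|---|---|
| 5% | 22.6% | 20.6% | 0.8 |
| 10% | 41.0% | 37.7% | 1.3 |
| 20% | 67.2% | 63.1% | 1.6 |

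Across both models, the pre-dose week adds about 0.4 to 1.6 of 40 patients to those who ever report a flu-like symptom. If individual reports are counted instead, the 40r column applies (0.4 to 4.0 patients with a pre-dose symptom).

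**5. Chronic symptoms.** The calculation assumes independence, so it does not cover patients with lasting fatigue, aching or redness. They would be positive before treatment and at many visits. Their number cannot be derived from the documents.

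**The case against.** A reader might infer that background and pre-dose symptoms simply count as imiquimod reactions. The protocol does not say so. Section 11.2 requires drug relation or onset after administration, and an adverse reaction also needs the Chief Investigator's causality assessment. Section 11.3 classes an event with incompatible timing as unrelated. A cold that began and ended before day 1 should fail on timing alone, provided that its onset is known. Whether the form records onset cannot be seen. This part of the objection stands.

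It does not remove the point. Section 11.1 presents the listed symptoms as likely to be related. Section 11.3 lets an event be called possible even if another cause could explain it, and counts it as related for notification. Chronic fatigue or redness that continues on treatment can pass that filter.

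The baseline photograph and the medical history are real pre-treatment references, so it would be wrong to say that nothing is recorded. But a photograph cannot show pain or discomfort, and a history need not ask these questions.

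The schedule of assessments in 4.1, as far as the extracted table can be read, marks adverse event recording at week 0. Section 9, to which the schedule refers for full requirements, describes no such assessment. The mark needs reconciling but does not supply a baseline.

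A reader might also take all background illness over the five visits as the size of the problem. Most of that illness arises during treatment, and a single baseline value would not remove it.

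**Conclusion.** The point holds as a minor design weakness. By the text of 4.1 and 9.2, the week 1 flu-like question includes about one pre-dose week, and this conflicts with the definition in 11.2. Neither flu-like symptoms nor the local reaction grade has a pre-treatment value, so existing symptoms can be counted as reactions.

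The estimate of 0.4 to 1.6 of 40 patients rests on assumed rates (1-10% per week, or 5-20% per recall window), on independence, and on a gap of about one week between the baseline visit and the first application. Model (b) also applies one rate to windows of different length. Chronic symptoms come on top and are not quantified. The outcome is a descriptive count, section 16.1 keeps the secondary outcomes in a secondary role, and the primary outcome is not affected.

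**What to change.** - At the existing week -1 visit, ask the same flu-like question and score the same local reaction scale.
- At week 1, ask about symptoms since the first application instead of since the last visit.
- Report reactions that are new or worse than baseline, next to the raw count.
- Reconcile section 9.2 with the week 0 adverse event mark in the schedule: either describe what is recorded then, or remove the mark.

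The cost is two baseline eCRF items at a visit that already takes place, one changed phrase and one extra reported count. Sample size and the primary outcome do not change. One limit remains: a baseline value will not separate a new intercurrent illness during treatment from a drug effect, so the new-or-worse count will still contain some background.
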